#### 7.4 Completion and submission of the case report form

For all patients requiring the completion of the case report form, the investigator will complete the case report form during the period from the start of treatment with Adcetris until the end of Cycle 4 and within 1 month after the end of Cycle 16, and submit it to the representative of Takeda.

If treatment with Adcetris is discontinued for any reason before the end of the observation period, the investigator will complete the case report form within 1 month after the completion of required observation submit it to the representative of Takeda. If treatment with Adcetris is discontinued due to any adverse event, however, the investigator will continue to observe the patient after treatment discontinuation until the adverse event resolves or improves wherever possible, and then complete the case report form and submit it to the representative of Takeda.

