## 9.2 Data to be recorded in Case Report Form

### 9.2.1 Cover sheet of Case Report Form

Date of the final completion of Case Report Form and name of the investigator completing Case Report Form

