###### 2) When to collect outcome measure data

After 16 cycles of treatment with Adcetris (or upon discontinuation of treatment with Adcetris)

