1.1.2 Efficacy analysis set

In this survey, the efficacy analysis set is defined as patients treated with Adcetris IV Infusion with no major protocol violation and evaluable for efficacy.

Definition

Term	Definition
This/the product	Refers to Adcetris for intravenous drip infusion in this Statistical Analysis Plan.
SOC	MedDRA/J System Organ Class
HLGT	MedDRA/J High Level Group Term
PT	MedDRA/J Preferred Term
LLT	MedDRA/J Lowest Level Term
Patients registered	Patients whose registration has been approved
Patients whose case report forms are available	Patients whose case report forms have been collected
Patients whose case report forms are not available	Patients registered but whose case report form have not been collected
Fixed patients	Patients whose case report forms are available, with the date of case report form completion entered in the PMS system
Non-fixed patients	Patients whose case report forms are available, with the date of case report form completion not entered in the PMS system
Safety analysis set	Fixed patients included in the safety analysis set
Safety analysis set (Hodgkin's lymphoma)	Patients included in the safety analysis set whose diagnosis is Hodgkin's lymphoma
Safety analysis set (anaplastic large-cell lymphoma)	Patients included in the safety analysis set whose diagnosis is anaplastic large-cell lymphoma
Patients excluded from the safety analysis set	Fixed patients excluded from the safety analysis set
Efficacy analysis set	Patients included in the safety analysis set who are also included in the efficacy analysis set
Patients excluded from the efficacy analysis set	Patients included in the safety analysis set who are excluded from the efficacy analysis set
Patients completing treatment	Patients completing 16 cycles of treatment with Adcetris
Patients discontinuing treatment	Patients not completing 16 cycles of treatment with Adcetris

Term	Definition
Adverse drug reactions, etc.	
Refers to “adverse drug reactions and infections.”
 
Adverse events not considered “not related” to Adcetris by the investigator.
 
In this Statistical Analysis Plan, the term “adverse drug reactions and infections” is used in titles and the term “adverse drug reactions, etc.” is used in text and tables.

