Days from the date of the last dose of Adcetris to hematopoietic stem cell transplantation (homologous) (Post-baseline hematopoietic stem cell transplantation: homologous)	For patients with post-baseline hematopoietic stem cell transplantation (homologous), this data item will be calculated using the following formula: date of hematopoietic stem cell transplantation (homologous) – date of the last dose of Adcetris + 1. If the date of post-baseline hematopoietic stem cell transplantation (homologous) is missing, this data item should be handled as missing. For patients with no post-baseline hematopoietic stem cell transplantation (homologous), this data item should be handled as missing.
Duration of treatment with Adcetris prior to hematopoietic stem cell transplantation (homologous) (Post-baseline hematopoietic stem cell transplantation: stem cell transplantation: homologous)	For patients with post-baseline hematopoietic stem cell transplantation (homologous), this data item will be calculated using the following formula: date of the last dose of Adcetris – date of the initial dose of Adcetris + 1. If the date of post-baseline hematopoietic stem cell transplantation (homologous) is missing, this data item should be handled as missing.

Term	Definition
homologous)	For patients with no post-baseline hematopoietic stem cell transplantation (homologous), this data item should be handled as missing.
Date of the final observation	“Date of the final observation” in the case report form If not provided, the most recent date entered in the case report form should be used.
Summary statistics	Number of patients, mean, standard deviation, minimum, 25th percentile, median, 75th percentile, and maximum.
Overall survival	Time to the date of death from any cause after the date of the initial dose of Adcetris. Surviving patients will be censored on the date of survival confirmation. The date of outcome of an adverse event with “Died/fetal” recorded in the Outcome field will be used as the date of death, and the final observation date will be used as the date of survival confirmation. The overall survival (date of death or survival confirmation) = date of death or survival confirmation – date of the initial dose of Adcetris+1
1 year	One year is defined as 365.25 days.
1 month	One month is defined as 30.4375 days.

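### The SAP's fallback for a missing final observation date does not exclude the form-completion date, so a survivor can be censored on a day when no observation was required

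*SAP*

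**What the plan says.** The definition table in SAP Section 1.0 fixes the censoring rule for overall survival in two steps: "Surviving patients will be censored on the date of survival confirmation", and "the final observation date will be used as the date of survival confirmation". Protocol Section 10.5.2 agrees. A separate entry in the same table defines the final observation date as the field of that name on the form and adds a fallback: "If not provided, the most recent date entered in the case report form should be used".

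Three other places bear on what that fallback returns:

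- Protocol Section 9.2.1 lists, as data on the form's cover sheet, "Date of the final completion of Case Report Form and name of the investigator completing Case Report Form".
- Protocol Section 7.4 places completion after observation. Forms are due within a month of the end of Cycle 16. For patients who stop early, "the investigator will complete the case report form within 1 month after the completion of required observation". Where an adverse event caused the stop, observation goes on where possible until the event resolves or improves, and the form is completed after that.
- Deaths enter the analysis only through an adverse event whose outcome is recorded as fatal (Protocol Section 10.5.2 and the SAP definition of overall survival).

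SAP Section 6.3 reports 1-year Kaplan-Meier survival with a two-sided 95% confidence interval, separately for the two lymphomas.

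**The concern.** A censoring date should be a day on which the patient was known to be alive. The fallback asks only for the latest date on the form. The form carries at least one date that describes the paperwork, and that date should not precede any clinical entry. Nothing in the SAP tells the programmer to skip it, and nothing in the protocol requires the patient to be seen, or confirmed alive, on that day.

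At stake is unobserved time counted as survival. If the patient died between last contact and form completion and the site did not learn of it, no fatal event is recorded. The patient then stays in the risk set for a period in which a death could not have been counted. The landmark makes this more visible: planned observation stops about a month before one year, and the permitted completion lag is about a month.

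**Working it through.** The plan states no survival figure to reproduce. Its one checkable calculation, the sample size in Protocol Section 3.2, does reproduce: with an 11% rate, P(at least 10 events) is 0.9518 at N = 140 and 0.9490 at N = 139. It has no bearing on this point.

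**Step 1: what the rule returns.** The fallback excludes no field, the completion date is a form entry, and completion follows observation. The latest date on a properly dated form can therefore be the completion date.

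**Step 2: how far censoring can move.** Inputs are 3-week cycles and 16 cycles (Protocol Section 7.1), and one year = 365.25 days and one month = 30.4375 days (SAP definitions). The first dose is day 1.

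- Dose 16 falls on day 1 + 15 × 21 = 316, and the cycle ends on day 316 + 20 = 336. This matches the SAP's last 21-day onset category, which ends at day 336.
- Distance to the landmark: 365.25 − 336 = 29.25 days.
- Latest permitted completion: 336 + 30.4375 = 366.4375, which is 1.1875 days past the landmark.
- Stopping on schedule after 15 cycles: 315 + 30.4375 = 345.4375, which is 19.8125 days short of it.

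On schedule and within the permitted month, only a 16-cycle completer can cross the landmark, and only if the form is finished in about the last day of that month. Delayed doses shift all these days later.

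**Step 3: direction.** Each recorded death multiplies the curve by 1 − 1/n, with n at risk. Extra censored time can only raise n at later deaths. As an illustration, n = 20 gives 0.9500 and n = 22 gives 0.9545. With the same recorded deaths, the estimate stays the same or rises.

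**Step 4: size, by simulation.** These assumptions are not in the documents: 140 patients, exponential survival, about 25% receiving 16 cycles and the rest spread evenly over 1 to 15, deaths after last contact not captured, dates missing at random, 1,500 replicates. Entries are the mean 1-year Kaplan-Meier estimate (%), with the mean number at risk at day 365.25 in brackets.

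| True 1-year survival | No fallback | 10% missing, 1-month lag | 10% missing, 180-day lag | 50% missing, 1-month lag | 50% missing, 180-day lag |
|---|---|---|---|---|---|
| 60 | 62.59 (0) | 62.95 (2.2) | 64.39 (5.6) | 64.16 (11.0) | 70.05 (28.3) |
| 75 | 76.80 (0) | 77.03 (2.7) | 78.18 (6.7) | 78.03 (13.4) | 81.55 (33.7) |
| 90 | 90.88 (0) | 90.91 (3.1) | 91.35 (7.7) | 91.20 (15.9) | 92.82 (38.8) |

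Three things help in reading the table:

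- The excess in the no-fallback column has another cause. Follow-up stops at day 336, where true survival is still 0.75^(336/365.25) = 76.75% in the middle row.
- With 10% missing and the permitted lag, the middle row moves by 77.03 − 76.80 = 0.23 points. The binomial standard error is √(0.75 × 0.25/140) = 3.66 points, so the Monte Carlo error of a difference is at least √2 × 3.66/√1500 = 0.13 points. The shift is close to simulation noise.
- For scale, the 95% half-width at N = 140 is 1.96 × 3.66 = 7.2 points, and wider within each lymphoma.

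**The case against.** The SAP never names the cover-sheet date. The fallback sits inside the definition of a final observation, so a sensible programmer may take it to mean the latest dose, test, scan or event. The final observation date is itself a scheduled form item for every patient (Protocol Section 9.2.4.3 and Appendix 1), so the fallback may never be used. Where treatment stopped for an adverse event, part of the gap before completion is real observation. Efficacy is collected for reference only (Protocol Section 2.0), and SAP Section 6.3 contains no test.

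Most of this stands and limits the size of the point. What does not stand is reliance on the sensible reading. The exclusion it needs is written nowhere, and the fallback is already an exception to the SAP's general rule against imputing missing data (Section 1.5).

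A reader might infer three stronger claims that the documents do not support:

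- *Every use of the fallback lands on the completion date, because all analysed patients have one.* The SAP does draw its analysis sets from patients described as "Patients whose case report forms are available, with the date of case report form completion entered in the PMS system". That describes a system entry used to classify forms. The documents do not say that it is the cover-sheet date or that it is among the dates searched.
- *The bias is concentrated in patients lost to follow-up or transferred.* Both are listed as reasons for discontinuation, but nothing says their final observation date is more often blank. A last-visit date can be entered for them.
- *The false follow-up runs to many months because forms are re-dated after queries.* No section describes re-dating, and Protocol Section 7.4 sets a one-month limit. The 180-day columns above are assumptions beyond the plan.

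**Conclusion.** The rule as written permits censoring on an administrative date, and no other section corrects it. For a patient who uses the fallback and was not observed in the gap, the effect on Kaplan-Meier survival is upward. This assumes that a death after last contact would go unrecorded; if sites reliably learned of such deaths, the bias would shrink or vanish.

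Within the protocol's own time limit, the added time is at most about 30 days per affected patient. An on-schedule 16-cycle completer is carried from about day 336 to at most about day 366, so the landmark is crossed only narrowly. The number of patients with a missing date is not given and may be zero. With few missing, the change in 1-year survival is a fraction of a point, far inside the confidence interval. The larger simulated shifts need many missing dates, longer lags than the protocol allows, or both. Because survival is a descriptive reference outcome, this is a minor correction.

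**What to change.** Replace the fallback sentence in the SAP definition of the final observation date with:

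> If not provided, use the latest dated patient contact recorded in the form (dose, laboratory test, imaging, transplantation, or adverse event onset or outcome date). Form completion and other administrative dates are not used.

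In addition, report with the survival table how many patients were censored by the fallback. That number settles whether the point mattered in practice.

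The cost is one sentence, a small programming change and one reported count. The downside is slightly shorter follow-up for the affected patients. The two supplemental plans contain only safety analyses and need no change.

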#### 9.2.5 Adverse events

##### 1) Outcome measures

Presence/absence of adverse events (see Table 1), adverse event terms, date of onset, CTCAE grade (the worst one), seriousness and its reason (see Table 2), (presence/absence and detail of) action taken to Adcetris, (presence/absence and detail of) intervention for adverse events, date of outcome, outcome, causal relationship with Adcetris\* (see Table 3), and changes in laboratory test values associated with adverse events over time

If the outcome is “not recovered/not resolved” or “unknown,” and the causal relationship with Adcetris is considered unevaluable, the event should be followed wherever possible.

\* If the event is considered not related to Adcetris, its rationale should be collected. If the causal relationship with Adcetris is considered unevaluable, its reason should be collected.

Note) Points to consider regarding adverse events

Worsening of the primary disease should not be regarded as an adverse event. However, abnormal worsening of the primary disease (e.g., worsening beyond the expected natural course of the disease) should be regarded as an adverse event.

Disease progression should be regarded as worsening of the primary disease rather than an adverse event. However, clinical or laboratory progression of an existing cancer (including new metastasis) that meets any of the criteria for the seriousness of adverse events (see Table 2) should be considered a serious adverse event.

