**Table 2 Criteria for the Seriousness of Adverse Events**

An adverse event meeting any of the following criteria will be considered serious:

1. Results in death.
2. Is life-threatening.
3. Requires inpatient hospitalization or prolongation of existing hospitalization.
4. Results in persistent or significant disability/incapacity.
5. Is a congenital anomaly/birth defect.
6. Is a medically important condition due to any of the above 1 to 5, including those listed in “Takeda Medically Significant AE List.”

Takeda Medically Significant AE List

•Acute respiratory failure/acute respiratory distress syndrome (ARDS)	•Anaphylactic shock
•Torsade de pointes/ventricular fibrillation/ventricular tachycardia	•Acute kidney failure
•Malignant hypertension	•Pulmonary hypertension
•Convulsive seizure (including convulsion and epilepsy)	•Pulmonary fibrosis (including interstitial pneumonia)
•Agranulocytosis	•Neuroleptic malignant syndrome/malignant hyperthermia
•Aplastic anemia	•Spontaneous abortion/stillbirth and fetal death
•Toxic epidermal necrolysis/oculomucocutaneous syndrome (Stevens-Johnson syndrome)	•(Suspected) transmission of infection via a drug
•Hepatic necrosis	•(Suspected) endotoxic shock
•Acute hepatic failure	

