#### 10.5.2 Overall survival

The time to death (regardless of the cause of death) will be analyzed using the “final observation date” in specified in Section 9.2.4.3 as the date of survival confirmation and the date of outcome of an adverse event with “Died/fetal” recorded in the Outcome field specified in Section 9.2.5 as the date of death

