4.0 Treatment Given

4.1 Treatment given

(1) Analysis sets to be used

Safety analysis set, safety analysis set (Hodgkin’s lymphoma), and safety analysis set (anaplastic large-cell lymphoma)

(2) Data to be analyzed

For each data item, patients will be stratified into the following categories below, and the frequency will be calculated. In addition, summary statistics of continuous variable will be calculated:

Data item	Category
Initial dose of Adcetris	<1.2 mg/kg, 1.2 mg/kg, >1.2 mg/kg to <1.8 mg/kg, 1.8 mg/kg, or >1.8 mg/kg
Mean dose of Adcetris	<1.2 mg/kg, 1.2 mg/kg, >1.2 mg/kg to <1.8 mg/kg, 1.8 mg/kg, or >1.8 mg/kg
Dose of Adcetris per 3 weeks	<1.2 mg/kg, 1.2 mg/kg, >1.2 mg/kg to <1.8 mg/kg, 1.8 mg/kg, or >1.8 mg/kg
Duration of treatment with Adcetris	1, 2, 3, 4, 5, 6, 7, 8, 9, 10, 11, 12, 13, 14, 15, 16, or ≥ 17 cycles
Reason(s) for discontinuation of Adcetris	Treatment goal achieved, adverse event(s), lost to follow-up, transfer to another hospital, pregnancy, inadequate response, and/or other
Post-baseline hematopoietic stem cell transplantation	Absent, present, or unknown
Type of post-baseline hematopoietic stem cell transplantation	Autologous or homologous
Days from the date of the last dose of Adcetris to hematopoietic stem cell transplantation (autologous) (Post-baseline hematopoietic stem cell transplantation: autologous)	-
Duration of treatment with Adcetris prior to	-

hematopoietic stem cell transplantation (autologous) (Post-baseline hematopoietic stem cell transplantation: autologous)	
Days from the date of the last dose of Adcetris to hematopoietic stem cell transplantation (homologous) (Post-baseline hematopoietic stem cell transplantation: homologous)	-
Duration of treatment with Adcetris prior to hematopoietic stem cell transplantation (homologous) (Post-baseline hematopoietic stem cell transplantation: homologous)	-
Drug(s) other than Adcetris used for the treatment of the primary disease	Absent or present
Drug(s) used for the prevention of infection	Absent or present
Specific drug(s) used for the prevention of infection	Antibiotics/synthetic antibacterial agents, antifungals, antivirals, trimethoprim-sulfamethoxazole combinations, and/or other prophylactics against infections

(3) Figure/table number

Tables 4.1-1 to 4.1-3

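### Overall survival is defined as all-cause, but deaths are found only through fatal adverse event outcomes and follow-up mostly ends at discontinuation or cycle 16, so some deaths may be censored as survival

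*SAP*

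**What the plan says.** **Endpoint.** The definitions table in SAP section 1 gives overall survival as "Time to the date of death from any cause after the date of the initial dose of Adcetris". Protocol 10.5.2 agrees: "The time to death (regardless of the cause of death) will be analyzed using the" final observation date and an adverse event outcome date.

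**Source of a death.** In both documents the date of death is the outcome date of an adverse event coded as fatal. In the SAP, the outcome date so "recorded in the Outcome field will be used as the date of death, and the final observation date will be used" to confirm survival. The protocol uses the final observation date "as the date of survival confirmation and the date of outcome of an adverse event with" a fatal outcome as the date of death. If the final observation date is blank, the SAP substitutes the latest date on the case report form.

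**What is an adverse event.** The note in Protocol 9.2.5 says "Disease progression should be regarded as worsening of the primary disease rather than an adverse event". The next sentence makes an exception for progression of an existing cancer "that meets any of the criteria for the seriousness of adverse events (see Table 2) should be considered a serious adverse event". The first criterion in Table 2 is "Results in death".

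**Windows.** Adverse events (9.2.5) and the final observation date (9.2.4.3) are collected up to the end of 16 cycles or discontinuation. Protocol 7.4 describes longer observation only after stopping because of an adverse event, until that event resolves or improves.

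**Discontinuation reasons.** SAP 4.1 tabulates "Treatment goal achieved, adverse event(s), lost to follow-up, transfer to another hospital, pregnancy, inadequate response, and/or other".

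**Output.** SAP 6.3 reports 1-year Kaplan-Meier survival with a 95% confidence interval and a plot for each of the two lymphomas.

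**The concern.** An all-cause endpoint should not depend on how the investigator classified a death. Here a death becomes an event only if someone entered it as an adverse event, and nothing in the listed items would reveal one that was missed. Section 9.2.4.3 asks for a date, not for status on that date, and the discontinuation categories name neither death nor progression.

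Two routes lead to a death being treated as survival. A site may read the 9.2.5 note as excluding lymphoma progression and enter no event. Or the patient may stop treatment and die after data collection has ended. The second route needs no site error. It is also informative censoring, because patients who stop for inadequate response probably have a worse prognosis than those who stay on treatment. At stake are the two Kaplan-Meier curves and the 1-year figures, which readers will take as all-cause survival in relapsed or refractory disease.

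**Working it through.** The documents state no survival rate, death count or precision target for overall survival, so there is no planned figure to reproduce. The 140 patients in Protocol 3.2 are sized on infusion reactions.

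**Step 1. Follow three deaths through the rules.**

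- *Lymphoma death during treatment, exception in 9.2.5 applied.* The death meets the first criterion in Table 2, is entered as a serious adverse event with a fatal outcome, and counts as an event. No bias.
- *Same death, site follows the statements that worsening of the primary disease and progression are not adverse events.* No event is entered. The patient is censored at the final observation date or, if that is blank, at the latest date on the form.
- *Patient stops for inadequate response and dies later.* Adverse event collection ended at discontinuation, and the extension in Protocol 7.4 does not apply. The patient is generally censored at discontinuation, whichever reading of 9.2.5 the site uses.

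**Step 2. Compare the window with the landmark.** Sixteen cycles of 3 weeks give 16 × 21 = 336 days. The SAP sets 1 year at 365.25 days. The gap is 365.25 − 336 = 29.25 days, so a patient treated exactly on schedule is censored about 29 days before the landmark. Only patients with delays or longer observation inform the curve at 1 year.

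**Step 3. Size if deaths are missed and censored at the time of death.** Assume true 1-year survival S = 0.75 and that a constant share f of deaths is missed over time. Kaplan-Meier then estimates S^(1 − f):

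- f = 0: 0.75^1.00 = 0.750
- f = 0.10: 0.75^0.90 = 0.772
- f = 0.25: 0.75^0.75 = 0.806
- f = 0.50: 0.75^0.50 = 0.866

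Both S and f are assumptions. Under full compliance with the exception, f is 0 for lymphoma deaths inside the window.

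**Step 4. Size if patients are censored at discontinuation.** Let λ be the yearly hazard of progression or discontinuation, a the death hazard before it and b the death hazard after it. Then:

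- True 1-year survival = e^−(λ+a) + [λ/(λ + a − b)] × [e^−b − e^−(λ+a)]
- Kaplan-Meier with censoring at discontinuation = e^−a

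For λ = 1.0, a = 0.05, b = 0.5, true survival is 0.3499 + (1/0.55) × (0.6065 − 0.3499) = 0.816, against a Kaplan-Meier value of e^−0.05 = 0.951. With λ from 0.5 to 1.5, a from 0.05 to 0.10 and b from 0.5 to 1.0, true survival runs from 0.62 to 0.87 and Kaplan-Meier gives 0.905 or 0.951. If b equals a, the two agree. None of these hazards is in the documents. The calculation shows direction and possible size only.

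**The case against.** The strongest reply is that the protocol already covers lymphoma deaths. The 9.2.5 note is a general rule followed by an exception, and fatal progression falls under the exception through the first criterion in Table 2. A reader might infer from the general rule alone that the plan directs lymphoma deaths to be censored as alive, and that reported survival is therefore overstated. The documents do not support that. Read as a whole, the note makes a lymphoma death within the window a reportable serious adverse event, and losing it needs a site to act on the contrary sentences. This part of the objection stands. What remains is a compliance risk: the note also says that worsening counts only when it goes beyond the expected natural course, about 100 institutions apply it on paper forms, and no death item would expose a miss.

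Three further points have weight:

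- The case report form is not among the documents, so the absence of a vital status item is inferred from the protocol's lists. The reasons in SAP 4.1 are tabulation categories that include inadequate response and other.
- Some patients stop because the treatment goal is achieved and may do better than average, so the net direction of the censoring bias is probable rather than certain. SAP 4.1 also allows for 17 or more cycles, so some follow-up may pass 336 days.
- Protocol 2.0 collects efficacy for reference only. Overall survival has no hypothesis, comparator or role in the sample size.

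None of this answers the truncated follow-up, which follows from the collection windows themselves.

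**Conclusion.** The point holds in this form: deaths for an all-cause endpoint come from a single source that depends on adverse event classification, the wording on progression pulls in opposite directions, and follow-up for most patients ends at discontinuation or at a nominal 336 days, before the 1-year landmark. Upward bias is probable, chiefly through informative censoring at discontinuation.

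Its size is unknown. The shift from 75% to 77%, 81% or 87% rests on an assumed survival rate and on assumed shares of missed deaths of 10%, 25% and 50%. At 0% there is no shift. The discontinuation example rests on assumed hazards.

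This should be fixed, but it does not threaten the safety objective, because survival is reference information.

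**What to change.** 1. In the SAP definition of overall survival and in Protocol 10.5.2, take the date of death from any case report form entry or site report, not only from an adverse event outcome.
2. Query sites once, for the roughly 140 patients with case report forms, for vital status, date and cause of death, and last-known-alive date through at least 1 year from first dose. Censor at the last-known-alive date. A status item dated at the final observation would not be enough, because it would miss later deaths. A new form item would not reach these patients either, since Protocol 8.0 says that the study has moved to enrollment only.
3. Reconcile the progression statements in Protocol 9.2.5.
4. Tabulate death and disease progression among the discontinuation reasons in SAP 4.1.
5. If the query cannot be done, label the estimate as survival counting only deaths recorded as adverse event outcomes during observation, and report the number censored at discontinuation before 1 year.

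The cost is one retrospective site query and minor changes of wording.

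### The overall survival curve is censored at the end of treatment observation for most survivors, so it does not estimate overall survival; the direction of the error depends on why patients stop

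*SAP*

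**What the plan says.** - **Endpoint and censoring.** The definitions table in SAP 1.0 defines overall survival as time from the initial dose to death from any cause. It continues: "Surviving patients will be censored on the date of survival confirmation", and "the final observation date will be used as the date of survival confirmation".
- **When that date is collected.** Protocol 9.2.4.3 gives the timing as "After 16 cycles of treatment with Adcetris (or upon discontinuation of treatment with Adcetris"), and Appendix 1 shows the same two time points. If the field is blank, the SAP says: "If not provided, the most recent date entered in the case report form should be used".
- **Deaths.** The only source of a death date is an adverse event with a fatal outcome, whose outcome date "recorded in the Outcome field will be used as the date of death". Protocol 9.2.5 collects adverse events until 16 cycles or discontinuation. Progression that meets a seriousness criterion, such as death, counts as a serious adverse event.
- **Exception.** Under Protocol 7.4, when treatment stops for an adverse event, "the investigator will continue to observe the patient after treatment discontinuation until the adverse event resolves or improves wherever possible".
- **Reasons for stopping.** SAP 4.1 codes them as "Treatment goal achieved, adverse event(s), lost to follow-up, transfer to another hospital, pregnancy, inadequate response, and/or other". The same table summarises transplantation after treatment, for example "Days from the date of the last dose of Adcetris to hematopoietic stem cell transplantation (autologous").
- **Analysis.** SAP 6.3 gives Kaplan-Meier 1-year survival with a two-sided 95% interval and a plot for each disease. It has no sensitivity analysis for the censoring and no breakdown of censoring by reason.

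**The concern.** Kaplan-Meier needs patients censored at a given time to have the same later death risk as those still under observation. Here the event that ends observation is usually the end of treatment, and patients stop treatment for reasons tied to prognosis. A patient with relapsed or refractory lymphoma who stops for inadequate response probably has a higher later death risk than one still on treatment. A patient who stops because the goal was reached may have a lower one. Neither group's later deaths nor later survival is normally captured.

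Without that information the curve describes what would happen if everyone who stopped had kept the death rate of those still on treatment. The 95% interval covers sampling error only. A reader of the final report would take a figure labelled overall survival as the survival of treated patients.

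This is separate from the length of observation. Sixteen cycles of 21 days are 336 days, and the SAP's year is 365.25 days, so a patient who finishes on schedule is censored 29.25 days before the 1-year point. Moving the landmark to 48 weeks would close that gap but leave this problem in place.

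**Working it through.** **Plan's own figures.** The documents give no survival assumption, precision or sample size for overall survival. The 140 patients come from infusion reactions: P(at least 10 of 140 at 11%) = 0.952, which reproduces the protocol but has no bearing on this curve. All death rates below are assumptions.

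**Check 1: closed form at 48 weeks (336 days).** Assume a death rate on treatment of 0.004 per week. A fraction p stops at a time uniform over weeks 6 to 40, after which the rate is multiplied by m.

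- Censoring at the stop, Kaplan-Meier estimates exp(−0.004 × 48) = 0.825.
- True 48-week survival of a stopper is exp(−0.192m) × (e^(40a) − e^(6a)) / (34a), with a = 0.004(m − 1).
- Error = p × (0.825 − stopper survival).

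| m after stop | Stopper survival | Error per stopper | Error, p = 20% | Error, p = 50% |
|---|---|---|---|---|
| 2 | 0.747 | +0.078 | +1.6 points | +3.9 points |
| 4 | 0.616 | +0.210 | +4.2 points | +10.5 points |
| 8 | 0.425 | +0.400 | +8.0 points | +20.0 points |
| 0.3 (good prognosis) | 0.885 | −0.060 | −1.2 points | −3.0 points |

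Errors add across groups, so mixed populations follow directly:

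- 20% poor at 4 times, 40% good: 0.2 × 21.0 − 0.4 × 6.0 = +1.8 points
- 20% poor at 2 times, 40% good: 0.2 × 7.8 − 0.4 × 6.0 = −0.8 points
- 10% poor at 4 times, 50% good: 0.1 × 21.0 − 0.5 × 6.0 = −0.9 points
- 10% poor at 2 times, 50% good: 0.1 × 7.8 − 0.5 × 6.0 = −2.2 points

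**Check 2: simulation, 400,000 patients per scenario.** Stops are uniform over days 21 to 300. Assumed annual death rates are 0.10 or 0.30 on treatment, 0.8 to 1.2 after inadequate response, 0.05 after goal achieved or transplantation, and 0.3 to 1.0 after an adverse event. The last two rows also count deaths within 90 days after an adverse-event stop, while survivors are censored at the stop.

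| Stops: inadequate response / goal or transplant / adverse event | On-treatment rate | True, day 335 | Kaplan-Meier | Difference |
|---|---|---|---|---|
| 50 / 0 / 0% | 0.10 | 0.732 | 0.912 | +0.18 |
| 25 / 40 / 20% | 0.10 | 0.815 | 0.913 | +0.10 |
| 10 / 50 / 20% | 0.30 | 0.792 | 0.758 | −0.03 |
| 0 / 60 / 0% | 0.30 | 0.818 | 0.760 | −0.06 |
| 25 / 25 / 30%, late deaths counted | 0.10 | 0.749 | 0.787 | +0.04 |
| 10 / 40 / 30%, late deaths counted | 0.10 | 0.802 | 0.784 | −0.02 |

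In every scenario the difference at day 20, before any stop, is zero.

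**The case against.** A reader might infer that the curve is biased upward throughout. The documents do not support that, for four reasons.

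1. Treatment goal achieved is a coded stopping reason, and transplantation after the last dose is recorded. These patients are censored by the same rule and push the curve down. The mix of reasons is not given, so it cannot be said that patients censored early are mainly those with the worst prognosis.
2. There is no bias before the first censoring.
3. Patients who stop for an adverse event are observed further where possible, and a blank final observation date is replaced by the latest date on the form. Some patients are therefore followed past the stop. A fatal outcome recorded in that time supplies a death date, and it too can lower the curve.
4. Protocol 2.0 makes safety the purpose and collects efficacy for reference. No comparison, test or sample size rests on this curve.

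All four stand, and they remove any fixed direction. They do not remove the defect. A patient who stops for inadequate response normally has no recorded follow-up afterwards, and 6.3 does nothing about it. Nor can the two effects be assumed to cancel. In check 1, one inadequate-response stopper at 4 times the rate (+0.210) outweighs about 2.4 good-prognosis stoppers who never die (0.088 each), and at 8 times about 4.6. At 2 times (+0.078) the two are about equal.

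It is also fair that best-case and worst-case bounds alone are wide. With 50% stopping in check 1, they run from 0.5 × 0.825 = 41% to 0.5 × 0.825 + 0.5 × 0.913 = 87%. They serve as the extremes, not as the main sensitivity result.

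**Conclusion.** The concern holds in limited form. For most survivors, overall survival is censored at the end of treatment observation. That censoring is likely informative, and the Kaplan-Meier estimate with its 95% interval does not represent overall survival of treated patients.

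The size rests wholly on assumed death rates and an assumed mix of stopping reasons. The 48-week error is about +2 to +20 points if 20 to 50% stop for inadequate response with a later rate 2 to 8 times higher and no good-prognosis stops offset it. It is near zero or a few points downward (to about −6 in the scenarios run) if stops for goal achieved or transplantation dominate. The documents do not show which applies.

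The correction should be made because it is cheap and the label is wrong as written. The effect on the study's safety purpose is limited.

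**What to change.** In SAP 6.3, and in the SAP 1.0 definition that it uses:

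1. Label the estimate and plot as survival during the Adcetris observation period, not overall survival.
2. Show numbers at risk under each curve. Tabulate the number censored by reason for discontinuation, including treatment goal achieved, with post-baseline transplantation shown separately. More than one reason can be recorded per patient, so state how such patients are counted.
3. Add a sensitivity analysis by stopping reason. Apply a range of assumed death rates after the stop, above and below the on-treatment rate, to patients censored before 48 weeks. Use all dying at censoring and all surviving to 48 weeks as the extremes. Apply it to every stopping reason, from each patient's actual censoring date, so that follow-up after an adverse-event stop is kept.
4. State that a figure called overall survival would need vital status for every patient regardless of treatment stop, which the current data collection does not provide.

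The cost is SAP wording and programming, since the stopping reasons and transplantation data are already collected. The reported figure becomes less definite and may be less favourable. New vital-status collection is not requested: it would mean going back to about 100 institutions that use paper forms, after the 140-patient enrolment has been reached.
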